# **CEAP Clinical classification of chronic venous disease**

The prevalence of CVD varies among the different stages of the disease. A large worldwide study of the Vein Consult Program showed a prevalence of clinically significant CVD of more than 60% in the general population (4). Varicose veins are the most common manifestation

of CVI with a prevalence up to 30% in adult population (1,2,3). The prevalence of active and healed ulcers is approximately 1% of the adult population (5). Since delayed healing and recurrence are very common, the prognosis of venous ulceration is poor (6).

The high prevalence and the chronic nature of venous disease have a considerable socioeconomic impact. A study conducted in the United States and the United Kingdom showed that venous ulcers cause a decrease of 2 million working days per year (7) and the National Health Service (NHS) spends approximately 1-3% of the total health care budget on the treatment of CVD (8,9).

Graded compression stockings are the primary conservative treatment in patients with CVI. A significant improvement can only be achieved with a good compliance (10). Reduced adherence to compression therapy is a well-known and major issue in the treatment of patients with CVD (13). Patients with clinical CEAP classification C4 venous disease, or higher, have an increased risk of venous ulceration. Non-compliance with compression hosiery and deterioration of the skin condition increases this risk. In literature the non-compliance ranged from 22%-67% (13 - 17). The most common reasons for non-compliance are inapplicability, the perception of inefficacy and the lack of comfort (13). However, the strategy to properly address non-compliance remains unknown.

Standard compression stockings reduce the symptoms of pain and oedema, facilitate the healing of ulcers, and prevent the recurrence of venous ulcers (11), but they do not improve the skin condition. Copper has been shown to promote angiogenesis and therefore it could support wound healing and possibly improve skin condition. Copper has also been shown to have strong antimicrobial properties. It has been shown in observational, non-randomised trials that improvement of the skin condition could be seen within two weeks (33,34). When no change in skin condition is seen within four weeks, it is unlikely to be seen at all.

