# Copper impregnated stockings

All patients will be asked to wear compression stockings (14-18mmHg). These closed-toe and below-the-knee stockings are made of 88% nylon, 5% elastin, and 7% spandex and come in various sizes. One of the pair will have copper oxide ions permanently attached to

CIVIL Protocol Version 3 (25/03/2015) 15/LO/0974

the nylon fibres and these stockings will contain 2-3% copper ions. The patients will wear a copper stocking on one leg (study leg) and a non-copper stocking on the other (control leg). Both the patients and the clinicians will be blinded to the copper impregnated stocking.

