# **Randomisation**

All stockings are marked with an 'L' for the left or 'R' for the right foot. The manufacturer has randomly marked the copper stockings with an 'L' or 'R' and paired these with a non-copper stocking. A closed envelope will contain the unique numbers of all the pairs of stockings and the information on which sock contains the copper. This envelope will remain closed for the whole recruitment period.

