# Patient data, history and physical examination:

Demographic data such as age, ethnicity, height and weight will be collected (Appendix 3 Datasheet). Past medical history such as concomitant (chronic) diseases and the use of medications will be obtained. At each visit, subjective symptoms will be obtained using the Aberdeen Varicose Veins Questionnaire (AVVQ). For obtaining objective signs, the CEAP classification and the Venous Clinical Severity Scoring (VCSS) will be performed for grading the severity of the venous insufficiency per leg individually, and photographs with the Eykona® 3D camera will be taken. All datasets will be coded and anonymised. The data will be stored in a secure room within the Trust. All electronic data will be stored within password protected IT system within the Trust, which is only accessible by the clinical and research team.

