#### Aberdeen Varicose Veins Questionnaire

This questionnaire is specific for varicose vein disease but it also addresses important elements of venous insufficiency in general. The AVVQ (appendix 4 Datasheet) is a validated questionnaire and it consists of 13 questions on signs and symptoms such as pain, oedema, itching, purple discoloration, eczema and skin ulceration. It also addresses social

CIVIL Protocol Version 3 (25/03/2015) 15/LO/0974

issues such as compression stocking usage and the effect of the disease on daily life. The AVVQ is the only validated questionnaire on vascular disease where most questions address each leg separately and therefore provides the ability to compare the two legs. The scoring of the questionnaire is from 0, which indicates no effect on the patient, to 100, which indicates a severe effect.

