# Venous Clinical Severity Scoring (VCSS)

The VCSS is an extension of the CEAP classification and has been designed as an evaluative tool for the assessment of CVD. The VCSS (appendix 4 Datasheet) consists of 10 categories, pain, varicose veins, oedema, skin pigmentation, inflammation, induration, ulceration (number, size and duration) and use of compression therapy, which are scored on a severity scale from 0 to 3.

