# Statistical analysis

Statistical analysis will be performed using SPSS version 20.0 or higher. The CEAP classification, the Venous Clinical Severity Score and the AVVQ score at the 2, 4, and 8 weeks assessment will be compared with the baseline scores. The length, width and surface area of the skin condition from the leg with the copper will be compared with the control leg and the measurements at the 2, 4, and 8 weeks assessment will be compared with the baseline measurements. Paired t-test will be used for continuous data at baseline and a multilevel (mixed) regression model will be used to analyse the change over time.

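### For AVVQ, VCSS and CEAP the analysis section states only a comparison with baseline, which cannot separate copper from the compression worn on both legs

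*Combined protocol and SAP*

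**What the plan says.** The design is a paired-leg comparison. Under Copper impregnated stockings, every patient wears compression of 14-18 mmHg on both legs, with copper in one stocking of the pair. Under Randomisation, "The manufacturer has randomly marked the copper stockings with an 'L' or 'R' and paired these with a non-copper stocking". The randomised contrast is therefore copper leg against control leg within a patient.

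The Statistical analysis section treats the outcomes in two ways:

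- For the two scores it says: "the Venous Clinical Severity Score and the AVVQ score at the 2, 4, and 8 weeks assessment will be compared with the baseline scores". CEAP is handled in the same way. No leg comparison is stated for these three.
- Skin length, width and surface area are compared between the copper and control legs and, separately, with baseline.

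The paired t-test is assigned to continuous data at baseline. For follow-up, "a multilevel (mixed) regression model will be used to analyse the change over time". The outcome, fixed terms and random effects of that model are not given.

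Leg-level data will exist. CEAP and VCSS are recorded for "grading the severity of the venous insufficiency per leg individually" (Patient data, history and physical examination). The AVVQ section justifies the questionnaire because "most questions address each leg separately and therefore provides the ability to compare the two legs".

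**The concern.** The primary objective concerns symptoms, and subjective symptoms are collected with the AVVQ. The outcome that serves the primary objective is thus among those with no stated randomised contrast.

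The background text on CEAP classification says that "Standard compression stockings reduce the symptoms of pain and oedema". Because both legs are compressed, a fall in score from baseline is expected with or without copper. VCSS has a further difficulty: its items include "use of compression therapy, which are scored on a severity scale from 0 to 3", so the score can move simply because the patient has started to wear the study stockings.

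Followed as written, the plan could report an improvement due to compression, time or regression to the mean in a form that reads as a copper effect. It would also not report the between-leg difference in symptoms, the quantity on which a larger paired-leg trial would be planned.

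**Working it through.** No stated figure is in dispute. The sample size of 15 is set by availability over three months, with no effect size, SD or power, so there is nothing to reproduce. The check has four steps. Correlations, compression effects and variance components are assumptions, since the documents give none.

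**1. Which comparison is stated for which outcome**

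| Outcome | Recorded per leg? | Versus baseline | Copper versus control |
|---|---|---|---|
| AVVQ | Most items | Stated | Not stated |
| VCSS | Yes | Stated | Not stated |
| CEAP | Yes | Stated | Not stated |
| Skin length, width, area | Yes | Stated | Stated, no baseline adjustment given |

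**2. What a before-after comparison can show**

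Let compression improve both legs by d (in SDs of change) and let copper do nothing. For a one-sample t-test on the copper leg's change, n = 15, two-sided 5%, 14 df, the noncentrality is d × √15.

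| d (assumed) | d × √15 | P(p<0.05), copper leg against baseline | P(p<0.05), copper minus control |
|---|---|---|---|
| 0 | 0 | 5% | about 5% |
| 0.3 | 1.16 | 19% | about 5% |
| 0.5 | 1.94 | 44% | about 5% |
| 0.8 | 3.10 | 82% | about 5% |

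Simulation (20,000 trials per setting, between-leg correlation of change 0.3, 0.5 and 0.7) agrees: the between-leg test rejects in 4.8% to 5.2% of trials throughout. The shared effect d cancels in the difference.

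**3. What baseline adjustment adds to the between-leg estimate**

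Let r be the correlation between the baseline and follow-up copper-minus-control differences, with equal SD s at both times.

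- Change score: variance 2s²(1 − r)/n.
- Adjusted: variance s²(1 − r²)/n × (1 + 1/(n − 3)). The last factor is the cost of estimating the slope, 13/12 at n = 15.
- Ratio, adjusted to change score: (1 + r)/2 × 13/12.

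| r (assumed) | Ratio | Variance | 95% CI width |
|---|---|---|---|
| 0.3 | 0.704 | 30% lower | 16% narrower |
| 0.5 | 0.8125 | 19% lower | 9% narrower |
| 0.7 | 0.921 | 8% lower | 4% narrower |
| 0.8 | 0.975 | 2.5% lower | 1% narrower |
| 0.9 | 1.029 | 3% higher | 2% wider |

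Break-even is at (1 + r)/2 = 12/13, so r = 0.846. The widths use t on 13 df (2.160) against 14 df (2.145). In simulation the adjusted estimate has type I error of 4.9% to 5.0% with t on 13 df, but 7.1% to 7.2% if 1.96 is used.

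**4. Whether any mixed model would do**

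Both legs are assessed at the same visit, so a visit-specific shift shared by the legs is plausible. It cancels in the paired difference. A model with only patient and leg-within-patient effects puts it into the residual. Simulations with 15 patients, no copper effect, and leg, residual and patient-by-visit variances of 0.5 each gave a week-8 model SE of 0.40 to 0.41 against a true SD of 0.33, with rejection of about 1% to 1.5% instead of 5%.

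The true SD can be checked by hand. The difference has variance 2 × (0.5 + 0.5) = 2 and r = 0.5, so the SD is √(2 × 0.75/15 × 13/12) = 0.33. Such a model would therefore lose precision unless it also has a patient-by-visit effect.

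**The case against.** The best defence is that the plan is brief rather than wrong. A mixed model for change over time can hold leg and leg-by-visit terms. The protocol names a study leg and a control leg, and it chose the AVVQ because it can compare legs. A between-leg comparison was probably intended. This stands as a statement about intent, but the section does not state that comparison for these outcomes, and its one explicit sentence about them names only baseline.

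The study is also a 15-patient pilot with no decision rule based on significance. That lowers the stakes of a single p-value, but not the need for the right contrast.

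Four stronger readings are tempting, and the documents do not support them:

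- *The plan has no between-leg comparison.* It states one for the skin measurements.
- *A wrong analysis will be run.* The model terms are unstated, so this cannot be known.
- *19%, 44% and 82% are the plan's false-positive rates.* The plan names no t-test on copper-leg change, and the AVVQ total is not a copper-leg score. The figures illustrate a possible misreading.
- *Baseline adjustment is needed for validity or for the later power calculation.* With the copper side randomised, an unadjusted change-score difference between legs is also valid. The SD and r can be computed from the collected data either way. Adjustment is a matter of precision, and the gain is negligible or negative at r of 0.8 or more.

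**Conclusion.** The concern holds as a gap in the stated analysis. For AVVQ, VCSS and CEAP the only comparison stated is with baseline, and that cannot attribute change to copper when both legs are compressed. The gap touches the primary objective and should be closed before the envelope is opened.

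That conclusion rests on the text alone. The size of the possible misattribution depends on an unknown compression effect, and the value of baseline adjustment depends on an unknown r. The appendix datasheet was not available, so a rule for scoring the AVVQ by leg may already exist there.

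**What to change.** In the Statistical analysis section, state the following:

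- For each leg-specific continuous outcome (VCSS per leg; a leg score from the leg-specific AVVQ items; skin length, width and area), the effect is the copper-minus-control difference at weeks 2, 4 and 8. It is estimated by regressing the within-patient difference on the uncentred baseline difference. The intercept, at zero baseline difference, is the estimate, with a 95% CI from t on 13 df if all 15 pairs are complete.
- The AVVQ leg-score rule, including what happens to items not asked per leg, is fixed before the envelope is opened.
- If a mixed model is preferred, it includes stocking-by-visit terms, patient, leg-within-patient and patient-by-visit effects, and small-sample degrees of freedom.
- CEAP is described by leg. Before-after results and the 0-100 AVVQ total are description only, not evidence for copper.
- The SD of the between-leg difference and its baseline-to-follow-up correlation are reported for planning.

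The cost is a few sentences, no new data and one degree of freedom. A pair is lost at any visit where one leg is not measured. The AVVQ leg score will not be the 0-100 total described in the protocol. If r is near 0.9, adjustment loses about 3% in variance at a single visit. The reported r will be imprecise: with 15 pairs, an estimate of 0.5 has a 95% CI of about -0.02 to 0.81.

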# Sample size calculation

The sample size for this study will be 15. This number is based on the prevalence of the disease in this hospital over three months' time. There is no existing data available to allow a sample size calculation. The data collection of this pilot study will enable power calculation for a larger multicentre study.

